4.4 Pausing and Resuming the Study

4.4.1 Criteria for Pausing the Study

The Protocol Chairs, in consultation with site PI, will closely monitor and analyze study data as they become available and will make determinations regarding the presence and severity of AEs. The administration of study products and new enrollments will be paused and the IND Sponsor will be promptly notified according to the following criteria:

- **One** (or more) subject experiences a **SAE** assessed as related to the study product (with or without adjuvant).
- **Two** (or more) subjects experience the same **Grade 3 or higher AE** assessed as related to the study product (with or without adjuvant). Pause is not required for self-limited solicited reactogenicity (generally defined as resolved within 2 days of onset) following any study vaccination.
- **Three** (or more) subjects experience the same or similar **Grade 3 solicited AE** (other than injection site redness or swelling) lasting ≥ 24 hours.

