4.4.2 Plan for Review of Pauses and Resuming the Study

Study randomizations and product administrations would resume only if review of the events that caused the pause resulted in a recommendation to permit further randomizations and product administrations. The review to make this decision will occur as follows:

- The IND Sponsor, with participation by the Protocol Chairs and site PI, will conduct the review and make the decision to resume or close the study for any SAEs or AEs that meet the criteria for pausing the study.
 - As part of the pause review, the reviewers will also advise on whether the study needs to be paused again for any subsequent AEs of the same type. The FDA and the IRB will be notified of SAE and Grade 3 or higher pause reviews and of the IND Sponsor's decisions.

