4.5.1 Discontinuation of Product Administrations

A subject may be discontinued from receiving study product for the following reasons:

1. Pregnancy;
2. Grade 3 adverse event assessed as related to the study product (with the exception that self-limited Grade 3 solicited reactogenicity does not require discontinuation of study injections);
3. Grade 4 adverse event assessed as related to the study product;
4. Immediate hypersensitivity reaction associated with the study product;
5. Intercurrent illness that is not expected to resolve prior to the next scheduled study product administration;
6. Treatment with systemic glucocorticoids (e.g., prednisone or other glucocorticoid) or other immunomodulators (other than nonsteroidal anti-inflammatory drugs [NSAIDs]), with the exception that study product administration may continue per site PI discretion if the next one occurs at least 2 weeks following completion of glucocorticoid treatment;
7. The IND Sponsor and/or PI assess that it is not in the best interest of the subject to continue receiving study product.

Subjects who receive at least one study product will continue follow-up according to the Schedule of Evaluations, except that the research sample collections will be discontinued for pregnant women or others in which it is contraindicated.

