Severity grading for hemoglobin decrease on the basis of the magnitude of decrease from baseline is not applicable at the grade 1 level; only absolute hemoglobin will be used to define grade 1 decrease. Increases in hemoglobin are AEs only for values above the upper limit of normal and are graded by the systemic illness clinical criteria.

Severity grading definition for Grade 4 local reaction to injectable product (Erythema/Redness and Induration/Swelling) included added text “requiring medical attention”.

1 X ULN was removed from the definition for PT increase.

When not otherwise specified in the table, the following guidance will be used to assign a severity grade:

Grade 1 (Mild): No effect on activities of daily living

Grade 2 (Moderate): Some interference with activity not requiring medical intervention

Grade 3 (Severe): Prevents daily activity and requires medical intervention

Grade 4 (Life-threatening): Hospitalization; immediate medical intervention or therapy required to prevent death.

Grade 5 (Death): Death is assigned a Grade 5 severity.

Only the single AE that is assessed as the primary cause of death should be assigned “grade 5” severity.

**Toxicity Grading Scale for Healthy Adult and Adolescent Volunteers Enrolled in
 Preventive Vaccine Clinical Trials
 FDA Guidance - September 2007**

A. Tables for Clinical Abnormalities

Local Reaction to Injectable Product	Mild (Grade 1)	Moderate (Grade 2)	Severe (Grade 3)	Potentially Life Threatening (Grade 4)
Pain	Does not interfere with activity	Repeated use of non-narcotic pain reliever > 24 hours or interferes with activity	Any use of narcotic pain reliever or prevents daily activity	Hospitalization
Tenderness	Mild discomfort to touch	Discomfort with movement	Significant discomfort at rest	Hospitalization
¹ Erythema/Redness	2.5 – 5 cm	5.1 – 10 cm	> 10 cm	Necrosis or exfoliative dermatitis requiring medical attention
² Induration/Swelling	2.5 – 5 cm and does not interfere with activity	5.1 – 10 cm or interferes with activity	> 10 cm or prevents daily activity	Necrosis requiring medical attention
³ Vital Signs				
	Mild (Grade 1)	Moderate (Grade 2)	Severe (Grade 3)	Potentially Life Threatening (Grade 4)
⁴ Fever (°C) (°F)	38.0 – 38.4 100.4 – 101.1	38.5 – 38.9 101.2 – 102.0	39.0 – 40 102.1 – 104	> 40 > 104
Tachycardia - beats per minute	101 – 115	116 – 130	> 130	Hospitalization for arrhythmia
⁵ Bradycardia - beats per Minute	50 – 54	45 – 49	< 45	Hospitalization for arrhythmia

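### Section 4.4.1: on its literal text, a related non-serious fever above 40 °C lasting 24 hours to about 2 days meets no automatic pause criterion, while three Grade 3 fevers of the same length do

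*Combined protocol and SAP*

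**What the plan says.** Section 4.4.1 of the combined protocol and SAP pauses dosing and enrolment on any of three criteria:

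1. One or more subjects with an SAE assessed as related.
2. Two or more subjects with the same related AE of Grade 3 or higher. The bullet ends with an exemption: "Pause is not required for self-limited solicited reactogenicity (generally defined as resolved within 2 days of onset) following any study vaccination".
3. Three or more subjects with the same or similar Grade 3 solicited AE, with the qualifier "other than injection site redness or swelling) lasting ≥ 24 hours". The words *or higher*, used in criterion 2, are absent. Relatedness is not required.

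The lead-in says that the Protocol Chairs, in consultation with the site PI, "will make determinations regarding the presence and severity of AEs".

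Temperature is one of the ten diary parameters in Section 4.2.7. The fever row of the Appendix IV table gives Grade 3 as "39.0 – 40 102.1 – 104" (°C, then °F) and Grade 4 as anything above that.

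The individual stopping rules in Section 4.5.1 are worded differently. Item 2 lists related Grade 3 events "with the exception that self-limited Grade 3 solicited reactogenicity does not require discontinuation of study injections". Item 3 lists "Grade 4 adverse event assessed as related to the study product", with no exemption.

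**The concern.** A pause rule should not become more lenient as severity rises. Here the exemption in criterion 2 has no upper grade and criterion 3 stops at Grade 3, so a Grade 4 solicited reaction can fall between them. Fever is the parameter for which this can realistically happen, because its Grade 4 needs only a thermometer reading.

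This is a first-in-human study, and a pause criterion exists to give a trigger that does not depend on someone choosing to act. In the gap, the only protection is discretionary. The dose-escalation reviews gate the steps to 30 and 60 mcg, so none follows once the 60 mcg groups open (10 subjects, 2 injections each, 20 planned injections).

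**Working it through.** The plan states no operating figure for the pause rules, so there is none to reproduce. The check is mainly one of logic.

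**Step 1. Does a Grade 4 fever have to be an SAE?** No. Under Section 5.2 an event is life-threatening only if it carried an immediate risk of death when it occurred. The general Appendix IV definition, "Grade 4 (Life-threatening): Hospitalization; immediate medical intervention or therapy required to prevent death", applies only where the table gives no specific grade, and the table does so for fever.

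**Step 2. Apply the criteria to a related, non-SAE fever.** Subjects needed for an automatic pause, with the exemption confined to criterion 2:

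| Duration | Grade 3, current text | Grade 4, current text | Grade 3, criterion 3 corrected | Grade 4, criterion 3 corrected |
|---|---|---|---|---|
| Under 24 h | none | none | none | none |
| 24 h to about 2 days | 3 (criterion 3) | none | 3 | 3 |
| Beyond about 2 days | 2 (criterion 2) | 2 (criterion 2) | 2 | 2 |

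Here *none* means that no number of subjects triggers a pause, even all 30. The inversion is confined to the middle row.

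**Step 3. How many diary parameters are affected?** Of the ten:

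- Seven have a Grade 4 defined by hospitalization or life-saving intervention (chills and arthralgia through the general definition). If related, these normally reach criterion 1 as SAEs.
- Two (redness and swelling) need necrosis, or for redness exfoliative dermatitis, which is unlikely to resolve within 2 days.
- One, fever, reaches Grade 4 by measurement alone.

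**Step 4. Size.** The documents give no rate of Grade 4 fever, so 0.5% and 1% per subject are assumed for Grade 4 fever lasting 24 hours to about 2 days, with no Grade 3 fever. With N = 30 (Section 6.3), the corrected criterion 3 pauses with probability

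P(X ≥ 3) = 1 − Σₖ₌₀² C(30, k) pᵏ (1 − p)³⁰⁻ᵏ

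- p = 0.005: 1 − (0.86038 + 0.12971 + 0.00945) = 0.0005, or 0.05%.
- p = 0.01: 1 − (0.73970 + 0.22415 + 0.03283) = 0.0033, or 0.33%.

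Under the current text both are 0.

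If Grade 3 fevers of the same length also occur, at an assumed 1% alongside 0.5% Grade 4, the current text pauses when there are at least three Grade 3 fevers (p = 0.01): 0.0033. The corrected text pauses when there are at least three of either grade (p = 0.015): 0.0101. The increase is 0.0101 − 0.0033 = 0.0068, or 0.68 percentage points.

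**Step 5. A mixed example.** Three 36-hour fevers, each peaking at 39.5 °C, meet criterion 3. If one peaks at 40.1 °C and each subject is counted at maximum grade, only two Grade 3 events remain and the criterion is not met.

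**The case against.** **The exemption may cover all three criteria.** Its sentence does not say that it is limited to criterion 2. Read broadly, a Grade 3 fever resolving within 2 days would not pause the study either, and the inversion disappears. But the sentence sits inside criterion 2, and on the broad reading the 24-hour threshold in criterion 3 would have almost no purpose. This is the weaker reading, though it cannot be ruled out.

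**The Chairs could count a Grade 4 fever under criterion 3.** Such a fever passes through the Grade 3 range, the criterion accepts similar events, and Section 4.4.1 does not say that a subject counts only at maximum grade (Section 6.4.3 says so for tabulation only). This stands as a possibility and weakens the mixed example. The text does not direct it, and the explicit *or higher* one bullet earlier points the other way.

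**Other safeguards are substantial.** They are:

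- Under Section 5.2 the investigator or sponsor may judge such a fever serious. If it is also related, one subject pauses the study, which is stricter than the Grade 3 rule.
- The exemption says only that a pause is not required, so a discretionary pause is open.
- Section 4.2.7 lists fever of 38.5 °C or higher for more than 24 hours as possibly needing clinical evaluation.
- Section 8.8.1 provides daily PI review and weekly review by the Protocol Safety Review Team (PSRT).
- Section 4.5.1 lists a related Grade 4 event as a ground for withholding that subject's next dose.

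All of this stands, and it is why the practical effect is small.

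**Section 4.4.2 proves less than it seems.** A reader might take "The FDA and the IRB will be notified of SAE and Grade 3 or higher pause reviews" as proof that criterion 3 was meant to include higher grades. It may refer only to criterion 2, which already does. Section 4.5.1 is the only real internal support for a wording slip, and it governs individual dosing, not the study pause.

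**Conclusion.** The inversion is present on the literal text, and it is narrow and infrequent. It needs a fever that is above 40 °C, assessed as related, not judged an SAE, and 24 hours to about 2 days long. It rests on the exemption applying only to criterion 2. The contrast with Section 4.5.1 items 2 and 3 suggests a slip and not a deliberate choice.

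A reader might infer that severe reactions in general escape the pause rules, or that subjects are left unprotected. The documents do not support either. The other nine diary parameters are normally caught at Grade 4 if related, and several discretionary safeguards apply to fever.

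The figures of 0.05% and 0.33% depend on assumed rates. The CHIKV VLP Phase 2 experience in Section 1.4.1 concerns a different vaccine and does not bound the rate here.

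Letters of Amendment 1 and 3 leave Section 4.4.1 unchanged. Letter 2 is not among the documents reviewed, so a change there cannot be excluded. This is a minor wording correction, worth making because it concerns a first-in-human safety trigger.

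**What to change.** In the third bullet of Section 4.4.1, insert *or higher* after *Grade 3*, and insert *Grade 3* before *injection site redness or swelling* in the exclusion. The 24-hour threshold and the count of three stay. This alone removes the inversion. The second insertion keeps Grade 3 redness and swelling excluded while letting their Grade 4 forms count.

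The cost is a few words and a slightly higher chance of a pause: 0.05 to 0.33 percentage points over 30 subjects at the assumed Grade 4 rates, or 0.68 points in the mixed case above.

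Two further changes are optional sponsor choices:

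- **Cap the criterion 2 exemption at Grade 3**, matching Section 4.5.1 item 2. Two related Grade 4 fevers would then pause the study even if each lasted under 24 hours, so this is a design preference. With both edits, the chance of a pause over 30 subjects is P(X ≥ 2) = 1.0% at an assumed 0.5% and 3.6% at 1% (Grade 4 fever only).
- **Record attribution for solicited events of Grade 3 or higher.** Criterion 2 requires relatedness, which Section 5.1 does not record for solicited events. This costs one database field.

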4.4.2 Plan for Review of Pauses and Resuming the Study

Study randomizations and product administrations would resume only if review of the events that caused the pause resulted in a recommendation to permit further randomizations and product administrations. The review to make this decision will occur as follows:

- The IND Sponsor, with participation by the Protocol Chairs and site PI, will conduct the review and make the decision to resume or close the study for any SAEs or AEs that meet the criteria for pausing the study.
 - As part of the pause review, the reviewers will also advise on whether the study needs to be paused again for any subsequent AEs of the same type. The FDA and the IRB will be notified of SAE and Grade 3 or higher pause reviews and of the IND Sponsor's decisions.

4.4.3 Dose-Limiting Toxicity

Dose-limiting toxicity is defined in this protocol as an AE that prevents a dose escalation of the study vaccine or prevents continuation of product administrations at a given dose level. If the study is paused as per criteria in [Section 4.4.1](#) and a decision is made to not resume the study vaccinations at the current dose, then the safety review will include a decision as to whether or not to continue accrual at a lower vaccine dose that was evaluated to be safe in order to achieve the target study accrual of 30 subjects.

4.5 Discontinuation of Product Administrations or Study Participation

Decisions to discontinue giving the second product administration or to discontinue protocol participation for a subject will be made by the site PI or designee.

4.5.1 Discontinuation of Product Administrations

A subject may be discontinued from receiving study product for the following reasons:

1. Pregnancy;
2. Grade 3 adverse event assessed as related to the study product (with the exception that self-limited Grade 3 solicited reactogenicity does not require discontinuation of study injections);
3. Grade 4 adverse event assessed as related to the study product;
4. Immediate hypersensitivity reaction associated with the study product;
5. Intercurrent illness that is not expected to resolve prior to the next scheduled study product administration;
6. Treatment with systemic glucocorticoids (e.g., prednisone or other glucocorticoid) or other immunomodulators (other than nonsteroidal anti-inflammatory drugs [NSAIDs]), with the exception that study product administration may continue per site PI discretion if the next one occurs at least 2 weeks following completion of glucocorticoid treatment;
7. The IND Sponsor and/or PI assess that it is not in the best interest of the subject to continue receiving study product.

Subjects who receive at least one study product will continue follow-up according to the Schedule of Evaluations, except that the research sample collections will be discontinued for pregnant women or others in which it is contraindicated.

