4.2.6 Product Administration

Before Ordering Study Product: Pregnancy prevention counseling must be conducted, and pregnancy test results must be confirmed negative for females of childbearing potential. Subjects must be clinically evaluated with a medical history review and injection site assessment. Blood samples must be collected after randomization but prior to product administration per Appendix III.

Ordering Study Products: The site must follow standard operating procedures to order study product from the Pharmacy.

Product Administration Procedures: It is recommended, but not required, that the first vaccination be administered into the non-dominant arm. It is preferred, but not required, to alternate arms for a subsequent product administration, if applicable. When choosing an arm for the product administration, clinicians should consider whether there is an arm injury, local skin problem or significant tattoo that precludes the administration of the study product or will interfere with evaluating the arm after product administration. All product administrations will be administered IM into upper arm deltoid muscle by needle and syringe.

For groups receiving adjuvant, the adjuvant will be added by the site pharmacist prior to delivery to the clinic for administration.

Prior to each product administration, the syringe MUST be inverted 5 times. “*Inversion*” of a prepared syringe is defined as a gentle, complete 180 degree rotation, do not “*shake*” the syringe.

For the Second Product Administration: If a subject presents with fever or other signs of significant illness on the day of the product administration visit, do not order or administer study product. Unscheduled visits may be used to evaluate the subject’s condition and the administration visit should be rescheduled within the allowable visit window.

If a subject is undergoing evaluation and/or treatment for a medical condition at the time of the second scheduled administration visit, then vaccinations should be delayed until the condition has resolved or is considered stable. Contact the IND Sponsor for questions about resuming or discontinuing vaccinations as needed.

To schedule a product administration visit outside of the allowable visit window, the site must document PI approval.

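### Section 4.5.1 makes withholding dose 2 optional after a related Grade 3 or 4 event, immediate hypersensitivity or immunomodulator treatment, although its own exceptions imply binding rules

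*Combined protocol and SAP*

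**What the plan says.** Section 4.5 leaves the decision on the second administration to the site: it "will be made by the site PI or designee". Section 4.5.1 then opens with "A subject may be discontinued from receiving study product for the following reasons" and lists seven grounds: (1) pregnancy, (2) related Grade 3 event, (3) related Grade 4 event, (4) immediate hypersensitivity, (5) intercurrent illness, (6) systemic glucocorticoids or other immunomodulators, and (7) a best-interest judgement by the Sponsor or PI.

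Two items carry exceptions. Item 2 ends "with the exception that self-limited Grade 3 solicited reactogenicity does not require discontinuation of study injections". Item 6 continues "with the exception that study product administration may continue per site PI discretion", on condition that the next dose falls at least 2 weeks after glucocorticoids are completed.

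Section 4.2.6 adds other controls on dose 2. Before product is ordered, "pregnancy test results must be confirmed negative for females of childbearing potential". Fever or significant illness on the day is a firm hold. If the subject is under evaluation or treatment for a condition, "then vaccinations should be delayed until the condition has resolved or is considered stable". Beyond that, the instruction is "Contact the IND Sponsor for questions about resuming or discontinuing vaccinations as needed".

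Section 4.4.1 pauses the whole study for one related SAE, for two subjects with the same related Grade 3 or higher event, or for three with the same or similar Grade 3 solicited event lasting at least 24 hours. It also explains what self-limited means: "Pause is not required for self-limited solicited reactogenicity (generally defined as resolved within 2 days of onset").

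**The concern.** The lead-in and the exceptions pull in opposite directions. Saying that one kind of Grade 3 reaction does not require stopping is needed only if other related Grade 3 events do. Granting PI discretion after a washout is needed only if the PI otherwise has none. For items 3 and 4 no exception shows the intent, so a binding meaning can only be inferred from where they stand in the list.

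This is a first-in-human trial with safety as its primary objective. On the literal reading, a second dose after a resolved product-associated hypersensitivity reaction complies with the protocol, and a monitor has no clear basis for calling it a deviation. The protocol writes firmer rules for comparable matters. Exclusion criterion 2 bars entry after any systemic immunosuppressive medication in the 14 days before randomization, yet the same treatment before dose 2 falls under the permissive list.

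**Working it through.** No figure in the plan states this point, so the main check is textual. Take one subject with one non-serious event after dose 1, and ask which rule stops dose 2.

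| Event in one subject | Pause under 4.4.1? | Barred by 4.2.6? | 4.5.1 read literally |
|---|---|---|---|
| Related Grade 3 AE, resolved by Week 8 | No, needs the same event in two subjects | No, once resolved or stable | Stopping optional |
| Related Grade 4 laboratory value, resolved or stable | No, same two-subject rule | No | Stopping optional |
| Immediate hypersensitivity, resolved | No, unless it is an SAE or the two-subject rule is met | No | Stopping optional |
| Glucocorticoid or immunomodulator treatment, condition stable | No, not a pause criterion | No | Stopping optional |
| Pregnancy | Not a pause criterion | Yes, negative test required | Optional, but moot |

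Section 4.4.2 governs resuming or closing the study after a pause and does not say whether the affected subject may be re-dosed. Section 8.8.1 provides daily PI review and weekly review by the Protocol Safety Review Team, but sets no individual stopping criterion. The two letters of amendment included in the document (numbers 1 and 3) do not touch Section 4.5.1.

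Size, as a loose guide only. Section 1.4.1 reports that all potentially related AEs in the phase 2 chikungunya VLP trial were mild to moderate, so 0 of 201 vaccinees had a related AE of Grade 3 or above.

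- Exact two-sided 95% upper bound: 1 − 0.025^(1/201) = 0.0182.
- Expected number among 30 subjects at that bound: 30 × 0.0182 = 0.55.
- Chance of at least one: 1 − (1 − 0.0182)^30 = 0.423.
- Chance of exactly one: 30 × 0.0182 × (1 − 0.0182)^29 = 0.320.
- Chance of two or more: 0.423 − 0.320 = 0.103.
- Share of trials with any event in which it is a lone event: 0.320 / 0.423 = 0.76.

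This bound is for a different product with no alum described, and it counts events after either dose, so it is not a dose-1 rate.

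Because no rate for this vaccine exists, here is the same calculation, 30p(1 − p)^29, at assumed per-subject rates for a given event:

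| Assumed rate | Exactly one of 30 | Two or more of 30 |
|---|---|---|
| 2% | 0.334 | 0.121 |
| 5% | 0.339 | 0.446 |
| 10% | 0.141 | 0.816 |

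At low rates, an event that occurs is usually a lone one, which the two-subject pause rule does not reach. That rule also requires the same event in both subjects, so where different events are pooled the two-or-more figure overstates how often it would act.

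**The case against.** The strongest reply is that the phrase is template wording for listing grounds. Section 4.5.2 uses the same permissive lead-in for voluntary withdrawal and for a stop by the Sponsor or regulators, neither of which is optional. Read together with the item 2 exception, a site could well treat other related Grade 3 events as stopping events. This stands, and it argues against reading the text as a deliberate licence to re-dose. It does not remove the ambiguity, because the same words can then be read either way.

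The second reply is that oversight fills the gap. Most clinical Grade 4 definitions in Appendix IV are hospitalizations, hence SAEs that pause the study if related. Section 5.2 names allergic bronchospasm needing intensive treatment as an SAE example. The PI, the safety review team and the Sponsor (through item 7) can all stop dosing. This also stands, and it limits the practical effect.

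The third reply is that a mandatory stop for every related Grade 3 event would catch a single systolic reading above 155 mm Hg, or a below-normal hemoglobin that had fallen 2.1 g/dL from baseline, if judged related. That is a real trade-off, and the fix below allows for it. The objection does not extend to immediate hypersensitivity, related Grade 4 events or item 6 with its stated exception.

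A reader might also draw stronger conclusions that the documents do not support:

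- That a pregnant subject may be vaccinated. Section 4.2.6 and footnote 4 of Appendix III require a confirmed negative test first.
- That Section 4.5.1 is the only control on dose 2. Sections 4.2.6 and 4.4.1 also act.
- That the 0.5% severe-headache rate in the chikungunya phase 2 trial sizes the problem. That headache followed the second of two vaccinations, so it could not bear on giving dose 2.
- That relatedness of solicited reactions is never judged. Appendix IV has the investigator assess it; Section 5.1 only leaves attribution for these events out of the database.

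**Conclusion.** The concern holds in a narrow form. Section 4.5.1 contradicts itself, and no other section requires dose 2 to be withheld after one non-serious related Grade 3 event, Grade 4 laboratory value or immediate hypersensitivity reaction. The text permits dose 2 in those cases; it does not direct it, and oversight makes it unlikely.

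Few subjects would be affected. The only observed rate of related Grade 3 or higher AEs in the phase 2 data cited is zero. The 1.8% bound assumes that the chikungunya vaccine's rate carries over. The documents give no rate for hypersensitivity or Grade 4 laboratory values. The conclusion rests on the wording and on the first-in-human setting. It is a cheap safety clarification that should be made, and it does not threaten the trial's analysis.

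**What to change.** Split the list in Section 4.5.1.

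- A subject **will be** discontinued from study product for pregnancy (to match Section 4.2.6), a related Grade 4 AE, an immediate hypersensitivity reaction associated with the product, or glucocorticoid or immunomodulator treatment, keeping the existing NSAID carve-out and 2-week exception.
- A subject **will be** discontinued for a related Grade 3 AE, with two exceptions. The first is self-limited solicited reactogenicity, defined as in Section 4.4.1 (generally resolved within 2 days of onset). The second is a transient, asymptomatic laboratory or vital-sign value that has resolved; here dose 2 may be given only with documented IND Sponsor agreement.
- A subject **may be** discontinued for intercurrent illness or on a best-interest judgement.

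The cost is a short amendment with IRB approval, and some loss of PI discretion. A related Grade 3 local reaction that is not self-limited would, for example, stop dosing. A stopped subject gives no dose-2 data, which is 1 of 5 (20%) in that group, but stays in follow-up, and Section 6.5 allows additional accrual to the group. Sample size, visit schedule and analysis do not change.
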